### 5.4 COEFFICIENT OF REPEATABILITY

Coefficient of repeatability (CR) between Screening and Baseline is calculated as 1.96 times the standard deviation of the differences between the two measurements of Screening and Baseline for each eye. The average of all the eye's CR will be used as a cut point to determine eye response.

## 5.5 CHANGE FROM BASELINE

The change from baseline value is defined as the value at a given time point minus the baseline value.

## 5.6 DERIVED VARIABLES

### ETDRS Score and LogMAR (on chart and off chart)

ETDRS score is calculated by the examiner and written on the source document worksheets and entered in the eCRF.

LogMAR (on chart and off chart) will all be derived in eCRF from the Snellen/decimal acuity.

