3 STUDY ENDPOINTS

3.1 Primary

The primary endpoint will be the ETDRS visual acuity (quantitative score) at Week 48 after IVT injection. The subjects' LogMAR scores, which are derived from the number of letters they read on the ETDRS chart, will be used for statistical analysis purposes. The change from baseline in each eye will be the primary response of interest.

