7.3.1 Visual Acuity

Enrolled subjects will include those able to read letters on the ETDRS chart ("on-chart" subjects) and those unable to read letters on the ETDRS chart but able to count fingers of the examiner at a given distance ("off-chart" subjects). On-chart subjects will have visual acuity measured with the ETDRS chart and an ETDRS score will be calculated. On-chart subjects will also have a Snellen acuity obtainable from the number of lines read on the ETDRS chart.

Off-chart subjects included in the study must maintain the visual ability to allow them to count fingers of the examiner as per the selection criteria. Off-chart subjects will not have an ETDRS score or a Snellen acuity obtainable from the ETDRS chart. Snellen acuity will be obtained utilizing the measured distance at which the subject was able to count the fingers of the examiner and a standardized formula available at (Karanjia 2014):

http://www.countfingers.com/

The Snellen acuities of on-chart and off-chart subjects will be converted to LogMAR for statistical analysis. Snellen acuities will be transformed to LogMAR using the standard formula available at:

http://www.myvisiontest.com/logmar.php

Additionally, 1 ETDRS line is considered equivalent to 0.1 LogMAR.

The visual testing at Visit 4 will be conducted for safety purposes and will not be analyzed as efficacy data (see Section 7.6.3).

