## **4. STUDY VARIABLES AND COVARIATES**

### **4.1 PRIMARY VARIABLE**

The primary endpoint will be the ETDRS visual acuity (quantitative score) at Week 48 after IVT injection. The subjects’ LogMAR scores, which are derived from the number of letters read on the ETDRS chart, will be used for statistical analysis purposes. LogMAR scores for subjects unable to read the ETDRS chart (i.e. off-chart subjects) will be obtained per the pre-defined Standard Operating Procedure and the protocol. The change from baseline in each eye will be the primary response of interest.

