## ETDRS/LogMAR and on-chart and off-chart:

- I. 1 ETDRS line = 5 letters
- II. 1 ETDRS line = 0.1 LogMAR
- III. 0.1 LogMAR = 5 ETDRS letters
- IV. 15 ETDRS letters = 0.3 LogMAR
- V. A less positive/more negative LogMAR is an improvement of vision
- VI. An increase in the number of ETDRS letters read is an improvement of vision

On-Chart subjects: defined as being able to read at least 3 ETDRS letters on a single line on the ETDRS chart at either 4 or 1 meters

- a. Have an obtainable Snellen equivalent obtained directly from ETDRS chart
- b. Each Snellen equivalent is assigned a LogMAR value

Off-chart Subjects: defined as a subject who cannot read at least 3 ETDRS letters on a single line of the ETDRS chart at either 4 or 1 meters and thus have no Snellen equivalent obtainable from ETDRS chart

- c. These subjects are categorized as able to either count fingers (CF), detect hand motion (HM), detect light perception (LP) or are no-light perception (NLP)
- d. For those categorized as either CF or HM a method for deriving LogMAR visual acuity is pre-specified
- e. The distance at which CF/HM vision was obtained is recorded per the standard operating procedure
- f. Study database derives the LogMAR based on this distance and the finger/hand dimensions of the examiner, per pre-specified method.

Treatment-Emergent Adverse Events (TEAE)

Treatment-emergent adverse events (TEAEs) are defined as AEs that started after study treatment administration at Visit 3 or that represent an exacerbation of a condition that is present at baseline after treatment administration. Worsening of visual acuity determined by the investigator to be due to progression of LHON will not be considered as an AE. Any AE with an unknown start date will be considered treatment-emergent if the event does not stop prior to study treatment administration. AEs with partial dates are described in [Section 5.7.2](#).

Prior and Concomitant Treatment

Prior treatments will be defined as any treatments with start date and time prior to the study treatment administration date and time.

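### On-chart LogMAR, the primary response, has two derivations (letters read, or Snellen lines read); under the line version the SAP's rule that 15 letters equal 0.3 LogMAR fails for individual eyes

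*SAP*

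**What the plan says.** **From letters.** Protocol 3.1 says the LogMAR scores used for analysis are those "which are derived from the number of letters they read on the ETDRS chart". SAP 4.1 has the same: "which are derived from the number of letters read on the ETDRS chart".

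**From Snellen lines.** SAP 5.6, under ETDRS Score and LogMAR, says "LogMAR (on chart and off chart) will all be derived in eCRF from the Snellen/decimal acuity". Protocol 7.3.1 says where the on-chart Snellen value comes from: "On-chart subjects will also have a Snellen acuity obtainable from the number of lines read on the ETDRS chart". It then adds: "The Snellen acuities of on-chart and off-chart subjects will be converted to LogMAR for statistical analysis". The later list in SAP 5.6 on on-chart and off-chart eyes says "Each Snellen equivalent is assigned a LogMAR value".

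**The letter-to-LogMAR equivalence.** The same list states "0.1 LogMAR = 5 ETDRS letters" and "15 ETDRS letters = 0.3 LogMAR". Three other places rely on it:
- SAP 3.3 bases its second power statement on 15 letters or 0.3 LogMAR.
- The main subject responder definition in SAP 5.6 accepts either 15 letters or 0.3 LogMAR between eyes.
- SAP 9.5.5 multiplies LogMAR effects by -50 to report letters.

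Neither document says which derivation governs, or how a partly read line is credited. Three letters on one line appears only as the test for being on chart. SAP 5.6 also says the ETDRS letter score is entered in the eCRF.

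**The concern.** Two programmers, one working from SAP 4.1 and the other from SAP 5.6, could build different primary datasets from the same charts. The letter version has steps of 0.02 LogMAR and the line version has steps of 0.1. The SAP's conversions between letters and LogMAR are exact for an individual eye only on the letter version.

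Two things are at stake: an unambiguous primary variable, and responder counts at 0.3 LogMAR that mean what the SAP says they mean. Protocol Appendix V allows no SAP amendment once the randomization code is broken, so the choice has to be fixed before then.

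**Working it through.** **Inputs.** 5 letters per line and 0.1 LogMAR per line (SAP 5.6), so 0.1/5 = 0.02 LogMAR per letter. SD of the between-eye difference in change 0.594, effect 0.3 LogMAR, 36 subjects, stated power 84% (SAP 3.3). Alpha 0.05, two-sided (SAP 9.5.1).

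**The plan's own figure.** Paired t-test with standardized effect 0.3/0.594 = 0.505 and n = 36: power 83.8%, which agrees with the stated 84%.

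**Loss of resolution.** Five successive letter totals share one line value. Totals up to 4 letters apart (4 × 0.02 = 0.08 LogMAR) therefore cannot be told apart at a given measurement.

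**Single-eye cut-off of 0.3.** Assume letters are read in order, a fixed number of letters earns a line, and the starting position within a line is uniform over its 5 places. A gain of d letters passes if it crosses at least 3 line boundaries. Counting over the 5 starting positions gives the same result whether a line needs 3 or 5 letters:

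| Gain (letters) | By letters | By lines |
|---|---|---|
| 10 | fail | 0% pass |
| 11 | fail | 20% pass |
| 12 | fail | 40% pass |
| 13 | fail | 60% pass |
| 14 | fail | 80% pass |
| 15 | pass | 100% pass |

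The table applies to gain from baseline (eye Criteria 4 and the on-chart arm of Criteria 13), to gain from nadir (Criteria 16), and to the between-eye LogMAR arm of the main subject responder definition. For eye Criteria 2 (loss of no more than 0.3), losses of 16, 17, 18 and 19 letters still count as response 80%, 60%, 40% and 20% of the time.

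**Subject Criteria 2.** This is a difference of two changes, so four rounded values enter. The same enumeration gives the following pass rates for the net difference in letters: 12, 42%; 13, 58%; 14, 72%; 15, 84%; 16, 92%; 17, 97%; 18, 99%. A net 14 letters often passes, but a net 15 fails 16% of the time and a net 16 fails 8%. The error runs both ways.

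**Letters not read in order.** A simulation with scattered misses credited a line at 3 or more of 5 letters. The slopes of the letter-recognition curve were assumed: 0.03, 0.06 and 0.10 LogMAR. Percentages passing the single-eye 0.3 gain:

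| True gain | Scoring | 0.03 | 0.06 | 0.10 |
|---|---|---|---|---|
| 0.20 | lines | 14.8 | 25.5 | 32.7 |
| 0.20 | letters | 0.4 | 3.2 | 7.6 |
| 0.40 | lines | 99.9 | 97.5 | 91.0 |
| 0.40 | letters | 99.9 | 98.8 | 95.9 |

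The shift is mostly towards response but not always: with the two shallower slopes, fewer eyes pass by lines at a true gain of 0.40.

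**Primary test.** Rounding variance per measurement is 0.1²/12 = 0.00083. Four measurements enter each paired difference: 4 × 0.00083 = 0.0033. Against 0.594² = 0.3528 this is +0.9%. The SD becomes √(0.3528 + 0.0033) = 0.597, and power falls from 83.8% to 83.5%.

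Under scattered misses the added noise is larger. The simulated SD of one eye's change goes from 0.035, 0.049 and 0.063 by letters to 0.055, 0.082 and 0.116 by lines. Twice the difference in variance is 0.0036, 0.0086 and 0.0190, or 1.0%, 2.5% and 5.4% of 0.3528. Power is then 83.4%, 82.9% and 81.9%. These figures treat 0.594 as letter-based and every eye as on chart, so they are upper ends for each scenario.

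**The case against.** The strongest reply is that there is only one chain. Letters read determine the line, the line gives the Snellen equivalent, and that gives LogMAR, so the endpoint sections merely summarise protocol 7.3.1 and SAP 5.6. Those sections give no per-letter formula, and the words Snellen/decimal acuity do not by themselves prove 0.1 steps. An Ophthalmic Evaluations Manual (protocol 7.3) and a Standard Operating Procedure (SAP 4.1) exist and may hold the detail. This has some force, but it does not rescue the plan. On that reading the line version governs, and the 15-letter equivalence still fails for individual eyes. SAP 4.1 cites the procedure for off-chart subjects only.

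The following parts of the reply stand:
- The 3-letter rule defines on-chart status; it is not a documented line-credit rule.
- Off-chart eyes have no letter score and are unaffected. So are the letter arm of Responder Definition 1 and all of Definition 2.
- The affected criteria carry no alpha: SAP 9.5.3 calls everything beyond the primary analysis supportive.
- The same scoring applies to GS010 and sham eyes under masking, and no bias in the treatment contrast is shown.
- Letter scoring has a cost of its own. Eyes reading 3 or 4 letters could score worse than the 1.6 LogMAR limit that SAP 5.6 also uses to define an on-chart eye.

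A reader might infer that every 0.3 cut-off is loosened and that every reclassified eye moves towards response. Subject Criteria 2 and the scattered-miss results contradict this. A reader might also want one percentage for all eyes misclassified. The documents do not give the share of eyes that are on chart, so none can be supported.

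**Conclusion.** The concern holds in limited form. On-chart LogMAR is derived in two ways that do not give the same values, and nothing says which governs. If lines govern, the SAP's letter equivalence fails for individual eyes, and most single-eye and between-eye 0.3 LogMAR criteria become easier to meet, with gains of 11 to 14 letters passing 20% to 80% of the time. Those percentages rest on letters read in order, a fixed line-credit threshold and a uniform starting position, none of which is in the documents.

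The effect on the primary test is small: about 0.3 points of power from rounding alone, and about 2 points (83.8% to 81.9%) under the least favourable slope simulated. A claim that the primary comparison is materially weakened or biased is not supported. The matter should still be corrected, because it concerns the definition of the primary variable and the repair is cheap.

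**What to change.** 1. In SAP 5.6 and protocol 7.3.1, derive LogMAR for on-chart eyes from the ETDRS letter score already entered in the eCRF, at 0.02 LogMAR per letter.
2. State the anchor. For example, 5 letters = 1.6 LogMAR fits the 20/800 limit in SAP 5.6 and gives LogMAR = 1.7 - 0.02 × letters. This anchor is an assumption for the sponsor to confirm.
3. Define on-chart status by the SAP's test of three letters on a single line, and reconcile the On-Chart LogMAR definition (1.6 or better) with it. With the anchor above, eyes reading 3 and 4 letters score 1.64 and 1.62. On-chart status feeds the on-chart and off-chart sensitivity analyses in SAP 9.5.1 and eye Criteria 12 and 13.
4. Keep the existing count-fingers and hand-motion method for off-chart eyes.
5. Align protocol 3.1 and 7.3.1 with SAP 4.1 and both parts of SAP 5.6, before the randomization code is broken.

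The cost is one derivation change and a small alignment of the on-chart definition. No new data are needed.

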#### On-Chart LogMAR

On-chart LogMAR eyes are defined as having a value of 20/800 or better (i.e. 1.6 LogMAR).

### LogCS

LogCS is obtained based on the last triplet where at least 2 of the 3 letters were read correctly on Pelli Robson chart and the LogCS is then entered in the eCRF.

#### On-Chart LogCS

On-chart LogCS eyes are defined as having a value of minimum 0 on the Pelli-Robson chart. If the eye is On-chart then a value is entered in the eCRF.

#### Total error score

Total error score is derived by the software and then entered into the eCRF.

### Responder

#### Eye Responder

##### Definition 1

Responder will be defined as an improvement of at least 15 letters in the ETDRS score compared to baseline, *or* being better than a Snellen acuity equivalent of 20/200. Early discontinuations will be considered as a non responder. For Week 96, two analyses will be performed: one for completers and one for subjects who don't have the Week 96 value available. If the Week 96 ETDRS score is not available, then the previous visit value will be used.

##### Definition 2

Responder will be defined by having an ETDRS Score equal to or greater than 20 letters. Early discontinuations will be considered as a non responder. For Week 96 two analyses will be performed: one for completers and one for subjects who don't have the Week 96 value available. If the Week 96 visual acuity score is not available, then the previous visit value will be used.

## Subject Responder

Responder will be defined as a subject whose ETDRS score of the treated eye is at least 15 letters better than the sham eye *or* whose treated eye has a LogMAR acuity of at least 0.3 LogMAR better than the sham eye. Early discontinuations will be considered as non responder. For Week 96, two analyses will be performed: one for completers and one for subjects who don't have the Week 96 value available. If the Week 96 visual acuity score is not available, then the previous visit value will be used.

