Leber Hereditary Optical Neuropathy (LHON) is an inherited mitochondrial disease of partial penetrance affecting both genders with predominance in males (~80%). The pathophysiology of LHON mainly affects the retinal ganglion cells (RGCs). The ND4 G11778A mutation is responsible for the majority of cases (~70%). Vision loss classically occurs in a bilateral sequential fashion, the second eye becoming involved after the first one with a median delay of 2 months. GenSight Biologics' strategy to specifically treat LHON is based on a gene therapy approach by the development of GS010. The scientific basis behind this Investigational Medicinal Product consists of rescuing mitochondrial function by reaching the nucleus of the target cell, forming intranuclear episomes that can be read and produce specific mRNA inducing ND4 protein synthesis and targeting of the ND4 protein to the mitochondria. This is expected to significantly improve the respiratory chain function. Preclinical studies performed in rats strongly suggest that GS010 displays a potential to restore wild-type ND4 expression.

Study Treatment: GS010 is a recombinant adeno-associated viral vector serotype 2 (rAAV2/2) containing the wild-type ND4 gene (rAAV2/2-ND4). In this study, subjects will receive a single dose of GS010 via intravitreal (IVT) injection containing 9E10 vg in 90µL balanced salt solution (BSS) plus 0.001% Pluronic F68[®].

Target Population:

The study population will be subjects with LHON due to the G11778A *ND4* mutation who have been affected by vision decline for 180 days or less.

Number of Subjects:

It is planned that approximately 40 subjects will be screened in order to randomize 36 into the study at 7 sites (one each in France, Germany, Italy, and the United Kingdom and 3 in the United States).

Objectives: Primary Objective:

To evaluate the efficacy of GS010 compared with sham at Week 48 in the change from baseline of the Log of the Minimal Angle of Resolution (LogMAR) in subjects affected for 6 months or less by LHON.

Secondary Objectives:

- To evaluate the efficacy of GS010 compared with sham over the follow-up period and at Week 96 in the change from baseline of the LogMAR.
- To verify whether the efficacy at Week 48 and at Week 96 of GS010 compared with sham and measured by the change from baseline in the LogMAR is dependent upon the treatment of the better- or worse-seeing-eye.

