5 POPULATION

The study population will include subjects with LHON due to the G11778A ND4 mutation with loss of vision in at least one eye for \leq 180 days in duration.

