## Subject Responder

### Criteria 1

Responder will be defined as a subject whose change of LogMAR from baseline in the treated eye is at least -0.2 better than the change from baseline of LogMAR in Sham eye. Early discontinuations will be considered as non-responders.

### Criteria 2

Responder will be defined as a subject whose change of LogMAR from baseline in the treated eye is at least -0.3 better than the change from baseline of LogMAR in Sham eye. Early discontinuations will be considered as non-responders.

### Criteria 3

Responder will be defined as a subject whose change of LogCS from baseline in the treated eye is at least +0.2 LogCS better than the change from baseline of LogCS in Sham eye. Early discontinuations (prior to W48 for the primary endpoint) will be considered as non-responders.

### Criteria 4

Responder will be defined as a subject whose change of LogCS from baseline in the treated eye is at least +0.3 LogCS better than the change from baseline of LogCS in Sham eye. Early discontinuations (prior to W48 for the primary endpoint) will be considered as non-responders.

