## Responder Analysis

### Subject responders

The responder analyses at Week 48, Week 72 and Week 96 will be based on a randomization test comparing the observed rate of responders to the expected rate of responders under  $H_0$  (i.e. absence of treatment effect). Expected rate is defined as responder rate in the Sham group based on an improvement of at least 15 letters in the ETDRS score compared to baseline or being greater than a Snellen acuity equivalent of 20/200.

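### The first-listed Subject Responder definition compares the two eyes at the visit without reference to baseline, so a gap of 0.3 LogMAR already present at entry can count as response

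*SAP*

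**What the plan says.** The first Subject Responder definition in SAP section 5.6 has two limbs joined by *or*. The letters limb reads: "Responder will be defined as a subject whose ETDRS score of the treated eye is at least 15 letters better than the sham eye". The LogMAR limb accepts a subject "whose treated eye has a LogMAR acuity of at least 0.3 LogMAR better than the sham eye". Neither limb mentions baseline.

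This does not look like shorthand, because neighbouring definitions name baseline where they mean it:

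- Eye Responder Definition 1: "Responder will be defined as an improvement of at least 15 letters in the ETDRS score compared to baseline", or better than 20/200.
- Criteria 2 under the additional Subject Responder definitions requires that the "change of LogMAR from baseline in the treated eye is at least -0.3 better than the change from baseline of LogMAR in Sham eye".

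SAP section 9.5.5 analyses subject responders at Weeks 48, 72 and 96 by "a randomization test comparing the observed rate of responders" with the rate expected under no effect. It does not say which subject definition is tested. It defines the expected rate as the sham-group rate of a 15-letter gain from baseline or acuity above 20/200, which is a single-eye event.

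On the disease, the Protocol study summary says: "Vision loss classically occurs in a bilateral sequential fashion, the second eye becoming involved after the first one with a median delay of 2 months". Protocol sections 5 and 5.2.1 admit subjects with vision loss in only one eye, and no listed criterion limits the difference between eyes. Protocol section 8.6 and SAP section 3.4 balance GS010 across better-seeing eyes by minimisation.

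**The concern.** Each subject is the unit, and the two eyes receive different treatments. A difference between the eyes at Week 48 is the sum of the difference at entry and the difference in change since entry. Only the second part can reflect treatment. The disease reaches the eyes one after the other and one-eye loss is eligible, so sizeable entry gaps are plausible.

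Take an entry gap of 0.5 LogMAR:

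- The better eye draws GS010 and neither eye changes. The treated eye is 0.5 ahead, so the subject is a responder.
- The worse eye draws GS010 and gains 0.7 relative to sham. It ends 0.7 - 0.5 = 0.2 ahead, so the subject is not a responder.

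A reported percentage of subject responders will be read as benefit. Under this rule it partly reflects asymmetry present before injection. The comparator in SAP section 9.5.5 does not take that out, because its event concerns one eye at a time and not the difference between two.

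**Working it through.** **Inputs from the documents.** Threshold 0.3 LogMAR = 15 letters (SAP 5.6). SD of the between-eye difference in change at Week 48 = 0.594, from the Phase I/II study (SAP 3.3). N = 36. Right eye allocated 1:1, with minimisation on better-seeing eye, so about half of subjects have the better eye treated.

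**Not in the documents.** The distribution of the entry gap, and how much of it persists to the visit. Both are varied below.

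**The plan's own figure.** The SAP states no rate for this endpoint. Its power figure for 0.594 does reproduce: 0.3/0.594 = 0.505, and a paired t-test with 36 subjects at two-sided 0.05 gives 83.8%, against the stated 84%.

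**Step 1: no change in either eye.** Every subject with a gap of at least 0.3 whose better eye drew GS010 is a responder; none whose worse eye drew it is. If a share q of subjects has such a gap, the rate is q/2.

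| q (assumed) | rate = q/2 | of 36 subjects |
|---|---|---|
| 10% | 5% | 1.8 |
| 25% | 12.5% | 4.5 |
| 50% | 25% | 9 |
| 75% | 37.5% | 13.5 |

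Under the change-based rule the rate is 0 in every row.

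**Step 2: chance change, no effect, gap fully persisting.** Let the between-eye difference in change be normal with mean 0 and SD 0.594, independent of the entry gap g. The visit-based rule gives:

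- better eye treated: Φ((g - 0.3)/0.594)
- worse eye treated: Φ((-g - 0.3)/0.594)

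The change-based rule gives Φ(-0.3/0.594) = 30.7% whichever eye is treated.

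| g | better eye treated | worse eye treated | average |
|---|---|---|---|
| 0.3 | 50.0% | 15.6% | 32.8% |
| 0.5 | 63.2% | 8.9% | 36.0% |
| 1.0 | 88.1% | 1.4% | 44.8% |

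**Step 3: partial persistence.** Let a fraction b of the entry gap remain at the visit without treatment. Take the gap as normal with mean 0 and SD s, and hold the SD of the difference in change at 0.594. The variance of the between-eye difference at the visit is then 0.594² + s²(2b - 1). With no effect, the visit-based rate is 1 - Φ(0.3/SD at visit). With a true 0.3 effect it is 50%. The rise from one to the other measures how well the rule separates effect from no effect. For the change-based rule the rise is 50 - 30.7 = 19 points.

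| s (assumed) | b = 1 | b = 0.5 | b = 0.25 |
|---|---|---|---|
| 0.3 | 17 | 19 | 21 |
| 0.6 | 14 | 19 | 26 |

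At b = 0.5 the extra term vanishes and the two rules tie. Above it the visit-based rule separates less well, and below it better.

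**Step 4: does the change-based rule depend on eye status?** With no effect, g = 0.5, b = 0.5 and s = 0.6, the residual SD is √(0.594² - 0.5² × 0.6²) = 0.513. The visit-based rule gives Φ((0.25 - 0.3)/0.513) = 46% with the better eye treated and Φ((-0.25 - 0.3)/0.513) = 14% with the worse eye treated. The change-based rule gives the reverse, 14% and 46%, because the sham eye's natural decline is then credited to the treated worse eye.

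**The case against.** The strongest reply turns the disease course against the concern. If the second eye follows the first, the better eye at entry should lose more by Week 48 and the gap should narrow. A fully persisting gap is then the extreme case, and zero change in both eyes over 48 weeks is unlikely in subjects within 180 days of onset. Step 3 bears this out: below half persistence the visit-based rule discriminates better. Step 4 shows that the change-based rule can also depend on eye status, in the opposite direction. The SAP already specifies change-based versions at 0.2 and 0.3, and section 9.5.3 treats everything beyond the primary endpoint analysis as supportive.

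This stands as a limit on size. It does not remove the fault that an existing gap is counted as response, nor the mismatch between the event and the expected rate in section 9.5.5.

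A reader might infer more than the documents support:

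- *That this is the headline definition.* It stands before the additional definitions, but the SAP does not call it main. The Protocol's responder endpoint is eye-level.
- *That responder status mostly records which eye drew GS010.* Even with full persistence, the entry gap accounts for s²/(s² + 0.594²) of the variance at the visit: 20%, 51% and 70% for s = 0.3, 0.6 and 0.9. The documents do not give s.
- *That it confounds the secondary question of better- versus worse-eye dependence.* Protocol 12.4.2 uses a homogeneity test for paired binary data, and Protocol 12.4.1 and SAP 9.5.1 use LogMAR models. None is stated to use this definition.
- *That allocation biases the rate.* Minimisation roughly equalises better-eye and worse-eye treatment. A true re-randomisation of eye labels would give even the visit-based rule a valid null, but section 9.5.5 sets the expected rate another way.

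**Conclusion.** The concern holds in limited form. As written, the first-listed Subject Responder definition counts an entry gap of 0.3 LogMAR or more as response when the better eye is treated, and requires the gap to be overcome when the worse eye is treated. The expected rate in SAP 9.5.5 does not cancel this, and that section leaves the tested definition unnamed.

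The size depends on two unknowns. With no change, the spurious rate is half the share of subjects with a qualifying gap. With chance change and a persisting 0.5 gap, the split by treated eye is 63% against 9%. Averaged over the two halves that is 36%, about 5 points above the change-based rule's 31%. The calculations assume normality, and carry over to these subjects an SD observed in the Phase I/II study. The loss of discrimination appears only if more than half the gap persists.

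The primary analysis uses change from baseline with baseline LogMAR as a covariate and is unaffected. This is worth correcting in a supportive endpoint; it is not a threat to the trial's main conclusion.

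**What to change.** - In SAP 9.5.5, name Criteria 2 of the additional Subject Responder definitions (difference in change from baseline of at least 0.3 LogMAR) as the definition tested.
- Compute the expected rate under no effect on that same definition, by re-randomising eye labels within subject under the allocation scheme used.
- Report the rate separately for subjects whose better eye and whose worse eye was treated, since Step 4 shows the change-based rule can also vary with eye status.
- Keep the visit-based count as a descriptive line.

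The change-based rule removes credit for the entry gap, but not chance response, which is still about 31% at an SD of 0.594. The re-randomised expected rate is therefore needed to read the result.

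The cost is SAP wording and a little extra analysis. Criteria 2 is already specified, though the documents do not say it has been programmed. The responder rate may turn out less favourable. Protocol Appendix V bars SAP amendments once the randomisation code is broken, so the change must come before the Week 48 unmasking.
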